6.2.4 CommanderFLEX™ In-Home Biometric Monitoring Equipment Sent to Subjects Home

This study will leverage Care Management Services (formerly Cardiocom) biometric monitoring equipment and nursing staff as part of the ISCC. Each enrolled subject will receive a CommanderFLEX™ device, including a weight scale, blood pressure cuff and console that will allow the subject to perform measurements of weight, blood pressure, and prompts the subject to answer Yes or No questions related to their HF symptoms (see Figure 2, Figure 3 and Table 9 in Section 3 for images and description and of the CommanderFLEX™ device and accessories). The CommanderFLEX™ kit will be provided at no cost, for use in their home during the length of the study. This kit will be drop shipped to the subject's place of residence after the subject has completed the baseline and programmer visit. At the end of the study, the subject will be required to return the CommanderFLEX™ and accessories.

6.3 C) Data Transmitted to ISCC

6.2.1 Daily CommanderFLEX™ Biometric Data

The subjects will be asked to collect daily blood pressure, weight and HF symptom information via the in-home CommanderFLEX™ kit they received after the baseline and programming visit. These data will be transmitted directly to ISCC. The ISCC nurse will place

a call to the subject at 5 days and then 21 days after the baseline and programming visit if the subject has not set-up the CommanderFLEX™ and encourage data transmission by the subject.

6.2.2 CRT-D Device Diagnostics Data

Once the silent OptiVol CareAlert is turned ON, the subject will not hear or notice anything different from their previous experience with their implanted CRT-D device. They can return to normal routines and activities. The CRT-D device will now monitor the subject's OptiVol Fluid Index for any threshold crossings. When the OptiVol Fluid Index value crosses the programmed threshold, the device will perform an automatic wireless CareLink transmission of the device diagnostics data to ISCC. The ISCC nurse will then make arrangements for the CRT-D device to transmit data at set intervals within the next 28 days to continue assessment of the fluid index for either therapy initiations, recovery criteria to stop medication intervention, and/or an OptiVol reset when applicable.

6.3 D) Risk Categorization and Intervention Determination

6.3.1 Subject Risk Categorization

Transmissions sent to the ISCC virtual CareLink-HF clinic integrate all device diagnostics data and assign a numerical value that corresponds to a risk status (Low, Medium or High). This risk status is based on OptiVol Fluid Index and other device diagnostics data (i.e. intrathoracic impedance, heart rate variability, activity, night heart rate, and other variables) using the published algorithm as described by Cowie et al.¹⁰ (Further information on this published algorithm is provided in the Section 2).

Upon receiving the transmission, the ISCC nurse will use the most recent value listed on the transmission record to categorize the numerical value provided by the algorithm to a corresponding risk status in the following way:

- Value is between 0 and less than 5.4 = Low
- Value is greater than or equal to 5.4 and less than 20 = Medium
- Value is greater than or equal to 20 = High

A transmission that is categorized as 'High' will result in an overall subject risk status of 'High' and the ISCC nurse will contact the subject for further assessment. When 'Medium' transmissions are received, the weight and HF symptom data from the previous 7-days are considered to determine if the overall subject risk status of the subject is 'High'.

For example, a transmission category of 'Medium' AND weight gain and/or symptom data indicating the presence of one or more HF symptoms from questions listed in Table 10, will assign the subject with an overall risk status of 'High' and the subject will be contacted by the ISCC nurse for further assessment. This will also be true for a subject that has a 'Medium' transmission AND the subject has weight gain of more than 2 pounds in one day or 5 pounds in 7 days.

Note: CareAlert transmission will arrive to the ISCC after 5 p.m. of the subject's time zone, therefore subject contact will be attempted the day following the receipt of transmission.

Table 10: Biometric HF Symptom Questions Collected by the CommanderFlex™

Questions in Table 10 will be asked of the subject by the CommanderFlex™ unit and collected/reviewed by the ISCC nurse when determining the overall risk status of a subject with a 'Medium' transmission.

Are you feeling more short of breath? If Yes then, Feel more short of breath with activity?
 
If Yes then, Are you more short of breath at rest?
 
If Yes then, Are you getting enough air?


Awaken during night short of breath? If Yes then, Feel more short of breath lying down?
 
If Yes then, Did you need extra pillows last night?
 
If Yes then, Did you sleep sitting up last night?

Are your ankles or feet more swollen?

Are you coughing more than usual? If Yes then, Is your cough different today?
 
If Yes then, Does lying flat cause coughing?

If the biometric or symptom data are missing from the day of the CareAlert transmission, the day the CareAlert transmission is reviewed, or the subject has provided less than three days of biometric data in the 7 days prior to receiving the CareAlert transmission, the ISCC nurse will contact the subject to assess the presence of HF related symptoms from questions outlined in Table 10. If any of these symptoms are present, the subject will be assigned an overall risk status of 'High' and further evaluation will be performed to assess if medication intervention is warranted (see section 6.3.2 for information on determining warranted intervention). If no weight gain or symptoms are present and the transmission is categorized as 'Medium' the subject status will be monitored remotely by the ISCC after receiving the transmission.

6.3.2 *Determining if Intervention is Warranted*

To ensure that the intervention is warranted, the ISCC nurse will first determine that the subject is not hypotensive per the following criteria. (If the subject is hypotensive a notification in the form of a 'Interim Patient Report' is sent to the site and intervention will not proceed).

- The subject has no signs of hypotension. For the subject to be considered hypotensive, systolic BP < 85 mmHg or diastolic BP <40 mmHg.

The ISCC nurse will also ask the subject a series of questions to ensure the OptiVol crossing is HF related.

- Have you had a CRT-D device change or lead revision?
- Have you been discharged from a hospital within the last 2 days and did you receive intravenous fluids for 1 or more days while in the hospital?
- Are you experiencing chills/shivering, shaking or muscle aches?
- Have you recently been treated for a COPD exacerbation?
- Any changes in baseline diuretic medication in the past 3 weeks?

If the subject answers YES to any of the above questions, the OptiVol crossing is deemed to not be HF related and the intervention will not proceed. Once the nurse has ensured that the OptiVol crossing is HF-related, the nurse will initiate the prescribed PRN intervention on file that was created at the baseline visit by the subject's investigator.

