6.5 F) Ensuring Subject Safety

6.5.1 Criterion for not initiating or continuing with a PRN Intervention

At the time of subject contact, (following the CareLink transmission and subject having been stratified as High risk), the ISCC nurse will make sure that the subject is not hypotensive based on the blood pressure measurement for the day of contact. If the subject has not yet transmitted the blood pressure measurement for the day of contact, the nurse will instruct the subject to obtain blood pressure measurement while on the phone. If the subject's systolic blood pressure is below 85 mmHG with associated hypotensive symptoms, the intervention will not be initiated. Additionally in the instance that the subject is unable or unwilling to provide a blood pressure measurement, the subject will be assessed for potential hypotensive symptoms – if positively reported, the medication intervention will not be initiated. ISCC will send an 'Interim Patient Report' to the subject's investigator noting the reason for not initiating PRN intervention. Subject's investigator will be required to further evaluate the subject, take necessary actions, and document them in eCRFs.

To ensure subject safety while a PRN intervention is underway, the subject's will be asked to provide a blood pressure and weight daily. If a predefined, physician specified, patient specific, safety threshold is crossed for either weight or blood pressure the subject will be

contacted by ISCC nurse. The nurse will telephonically evaluate the subject for symptoms known to suggest that intervention may not be safe (Table 11). If any one of the two symptoms is present, PRN will be stopped and the investigator will be sent an 'Exception Report' to assist with further subject follow-up (see Appendix B: ISCC Reports to Physician for an example of this report). The ISCC nurse will make one attempt to establish the contact with subject to evaluate subject symptoms to potentially stop PRN intervention. If the nurse is unable to establish the subject contact, a report will be sent to the investigator and/or phone call will be made to the site to notify that values were outside threshold(s).

Table 11: Safety Thresholds for Cessation of Medication Intervention (PRN)

PRN Cessation and Safety Threshold(s):			
Hold/Discontinue PRN Diuretic use if telephonically assessed to have met Weight or BP threshold and Symptom(s):			

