Weight Loss:	Weight < 150lbs: 3 lbs/2days Weight 151-300lbs: 4 lbs/2 days Weight > 301lbs: 5 lbs/2days	Or	____ lbs/ ____ days (Physician specified range)
OR			
Blood Pressure:	Systolic of < 85 mmHG or a diastolic of <40 mmHg	Or	< ____ / ____ mmHg (Physician specified value)
AND			
Telephonically Assessed Symptom(s):	New lightheadedness when moving from sitting to standing or Muscle cramping or Charlie horses		

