6.5.1.2 Safety Monitoring Using External Biometric Data

Outside of the PRN medication intervention window, subject's blood pressure will be monitored for hypotension per nominal safety threshold of a systolic blood pressure of <85 mmHG or a diastolic blood pressure <40 mm Hg or physician specified threshold, if different. If the hypotension criterion is met, subject will be contacted and assessed for presence of two hypotensive symptoms. These hypotensive symptoms will be assessed by asking the following two questions: Are they experiencing new lightheadedness when moving from sitting to standing? And, are they experiencing any cramping or Charlie horses? If any of the two symptoms or both symptoms are present, the subject will be asked to contact their physician. An 'Exception Report' will be sent to the investigator including a note about their patient's safety issue (see Appendix B: ISCC Reports to Physician for an example of this report). The Investigator will be required to review the report and determine if clinical actions are necessary. Actions along with rationale will be documented in the eCRF. If no actions are needed, rationale for that will also be recorded in the eCRF. If the action is updating of HF medications or PRN prescription, updated medication and PRN forms will be sent to ISCC within 24 hours. Lack of completing eCFR in its entirety will be considered a protocol deviation.

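### The checks for starting a PRN ignore a physician's blood-pressure limit set above 85/40 mmHg, so extra diuretic can be started in a state where Table 11 says to hold it

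*Protocol*

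**What the plan says.** Under Protocol 6.2.1 the investigator sets subject-specific blood-pressure and weight-loss parameters at the baseline visit, before any PRN. Four later rules use blood pressure.

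- **Start, 6.3.2.** The nurse first confirms that the subject is not hypotensive: "For the subject to be considered hypotensive, systolic BP < 85 mmHg or diastolic BP <40 mmHg". Five questions follow, to confirm that the OptiVol crossing is HF-related. None asks about lightheadedness. Once the crossing is judged HF-related, "the nurse will initiate the prescribed PRN intervention on file that was created at the baseline visit".
- **Start, 6.5.1, first paragraph.** If the subject's "systolic blood pressure is below 85 mmHG with associated hypotensive symptoms, the intervention will not be initiated". If the subject cannot or will not give a reading, hypotensive symptoms alone bar the start.
- **PRN underway, 6.5.1 and Table 11.** The instruction begins "Hold/Discontinue PRN Diuretic use if telephonically assessed to have met Weight" and goes on to require the weight or blood-pressure threshold together with a symptom. The blood-pressure threshold is 85/40 or a "Physician specified value". The symptoms are "New lightheadedness when moving from sitting to standing or Muscle cramping or Charlie horses".
- **Outside the PRN window, 6.5.1.2.** Monitoring uses 85/40 "or physician specified threshold, if different". If the limit is crossed and a symptom is present, "the subject will be asked to contact their physician" and an Exception Report goes to the investigator.

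**The concern.** The physician's limit governs stopping a PRN and background monitoring, but not the decision to start. That decision is made by a nurse on the telephone under a standing order, and the investigator is told afterwards that the PRN has begun (6.4.1). The baseline limit is therefore a main route by which the physician's judgement about blood pressure could act before the first dose, and the start rules leave it out.

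What is at stake is first patient safety: a lightheaded subject below his or her own limit may be given more diuretic. There is also an inconsistency. A lightheaded subject who gives no reading is not started, while one who gives a reading below the physician's limit can be. Second, an episode started this way and then stopped for hypotension fails the first criterion of the safety endpoint (13.4.2).

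**Working it through.** This is a question of decision rules, so there is no planned figure to reproduce. The rules can be compared directly.

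**Rules as written** (S = systolic, D = diastolic, in mmHg)

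- 6.3.2 bars the start if S < 85 or D < 40.
- 6.5.1 bars the start if S < 85 and symptoms are present.
- Table 11 holds the drug if (S or D is below its limit) and a symptom is present. The limit is 85/40 or the physician's value. I take either number falling below the physician's value as a crossing, as in the nominal rule.

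**Individual states**

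| Reading and symptoms | 6.3.2 | 6.5.1 | Table 11, limit 95/50 |
|---|---|---|---|
| 92/60, lightheaded | not barred | not barred | hold |
| 82/60, none | barred | not barred | no hold |
| 82/60, lightheaded | barred | barred | hold |
| 95/38, none | barred | not barred | no hold |
| 95/38, lightheaded | barred | not barred | hold |

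The first row is the gap. Rows two, four and five show where the two start checks differ.

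**All states.** I listed every whole-number reading with S from 70 to 130, D from 30 to 90 and D below S, for a lightheaded subject. I then kept those that pass both start checks but meet Table 11. The documents give no physician-set values, so the limits are illustrative.

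| Physician limit | Readings in the gap |
|---|---|
| 85/40 (nominal) | none |
| 80/40 | none |
| 90/40 | S 85–89 |
| 90/50 | S 85–89 or D 40–49 |
| 95/50 | S 85–94 or D 40–49 |
| 100/60 | S 85–99 or D 40–59 |

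In the last four rows the readings must also pass 6.3.2 (S at least 85, D at least 40). The gap therefore opens when the physician's limit exceeds 85 systolic or 40 diastolic, and not otherwise.

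**Which symptom.** The case rests on lightheadedness. A subject with cramps may answer yes to the 6.3.2 question that covers muscle aches and be excluded that way.

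**Size.** Protocol 13.1 expects about 105 PRN episodes. The three shares below are assumptions, not figures from the documents:

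episodes affected = 105 × (share in subjects with a raised limit) × (share of those with a reading between nominal and that limit) × (share of those with lightheadedness)

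- Low: 105 × 0.10 × 0.02 × 0.10 = 0.02
- Mid: 105 × 0.25 × 0.08 × 0.20 = 0.42
- High: 105 × 0.50 × 0.20 × 0.30 = 3.15

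Each such episode that is then stopped lowers the observed safety rate by 1/105 = 0.95 percentage points.

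**The case against.** The best reply is that other text would catch the case. Before a PRN starts the subject is outside the PRN window, so 6.5.1.2 applies the physician's limit, and the nurse on the contact call could meet both rules at once. The harm requires that nurse to refer the subject for low blood pressure and start the diuretic anyway. This makes the event less likely. However, 6.5.1.2 ends in advice and a report, and nothing in it withholds the PRN.

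Table 11 might also be read as covering the start, since it speaks of holding the drug and sits under a heading that includes not initiating. But its title refers to cessation, the text introducing it concerns a PRN already underway, and the explicit start text uses fixed numbers. If the start rule depends on this inference, it should be written out.

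Other points stand in part:

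- Exposure may be short, because Table 11 applies once the PRN is underway. The nurse makes only one contact attempt, although a failed attempt leads to a report or call to the site.
- The two start checks are both bars. Applied together, they block 82/60 and 95/38, so their disagreement creates no unsafe state unless a nurse relies on 6.5.1 alone.
- The enrollment exclusion at systolic below 90 (5.2.2) makes a limit above 85 plausible but does not show that investigators would set one.
- The nurse scripts are not in the documents, so actual practice may be tighter than the text.
- Scoring a stopped episode as not safe is the endpoint working as intended.

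**Conclusion.** The concern holds. Followed as written, the protocol allows a PRN to be started in a state where its own Table 11 says to hold it, whenever the physician's limit is above 85/40, the reading lies between the two and the subject is lightheaded. With limits at or below 85/40 there is no gap.

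The numerical effect is probably well under one episode in the study (0.4 in the mid case), and that figure rests wholly on assumed shares. The case for change is therefore safety and a clear rule for the nurses rather than bias in the safety rate. The change should be made. Confidence is medium, because the physician-set limits and the nurse scripts cannot be seen.

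**What to change.** State one start rule, in identical words, in 6.3.2 and in the first paragraph of 6.5.1: do not start a PRN if systolic is below 85 or diastolic below 40 mmHg, or if either value is below a higher physician-specified limit and a Table 11 symptom is present. Keep 85/40 as the floor when the physician's limit is lower, and keep the existing symptoms-only bar for subjects who give no reading.

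With this rule no blood-pressure reading can meet Table 11 and still pass the start check, and the two sections agree on the diastolic limit and on when symptoms are needed.

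The cost is one sentence in each section and an update to the nurse script. The limit is already recorded at baseline, blood pressure is already checked at contact, and 6.5.1.2 already has the nurse ask both symptom questions when the physician's limit is crossed.

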6.4 E) Interventions

The medication intervention will have two components. The first component is the ISCC acute medication intervention for acute volume management executed by ISCC as per investigator's standing orders (left arm in Figure 5 below and Section 6.4.1). In addition, the ISCC nurse will perform dietary and medication counseling when applicable.

The second component of the medication intervention will be the responsibility of the investigator (right arm in Figure 5 below and Section 6.4.2). ISCC will provide notifications to the participating site to alert the investigator when a re-evaluation of the subject's chronic medication is requested (see Appendix B: ISCC Reports to Physician for an example of this report).

[figure not shown]

Figure 5: Intervention in INTERVENE-HF study.

The Intervention for this study has two components: ISCC executed intervention (left arm) and Investigator executed intervention (right arm).

6.4.1 ISCC Executed Acute Medication Intervention (PRN and Counseling)

The ISCC facilitated intervention component will consist of providing reinforcement and direction to the subject as to when they are to self-administer up to two rounds of investigator prescribed PRN to the subject per single transmission that warrants action. The investigator prescribed PRN is initiated after ISCC nurse has ensured that subject has been compliant with their baseline medication regimen including diuretic medications. Each round of PRN will be 3 days long. Thus, no more than 6 days of PRN medication will be administered to the subject.

The example scenario in Figure 6 below is an illustration of this ISCC executed intervention. Referring to Figure 6, the day of the transmission is considered Day 0. Since the OptiVol CareAlert transmission is initiated by the device at 5 PM, the nurse will attempt to contact the patient on the following day (includes weekends). Thus, the ISCC nurse will call the subject via phone on Day 1 (1 day post initial transmission), and upon subject contact, guide the subject to take their first round of investigator prescribed diuretic for 3 days if intervention is warranted (Section 6.3.2 above).

The ISCC nurse will notify the subject's investigator using a 'Interim Patient Report' indicating that the first round of PRN has been initiated (see Appendix B: ISCC Reports to Physician for an example of this report).

One Round of Medication Intervention

[figure not shown]

Figure 6: Example Scenario of One Round of Medication Intervention (PRN).

The efficacy of the PRN is evaluated using raw impedance based recovery criterion. (Refer to section 6.4.1.1 and Figure 8 for a detailed description of determining recover criterion.) Recovery criterion is evaluated on Day 4 (when possible) (4 days post initial transmission or 3 days post PRN initiation) and then again on day 8 (when possible) after first PRN. If the recovery criterion is not met on day 4, a second round of PRN is initiated. The ISCC nurse will notify the subject's investigator using a 'Interim Patient Report' indicating that the second round of PRN has been initiated. Figure 7 illustrates this example scenario of 2 rounds of successive PRNs.

Two Rounds of Medication Intervention

[figure not shown]

Figure 7: Example Scenario of Two Rounds of Medication Intervention (PRN).

The efficacy of the second round of PRN will be evaluated on Day 8 (when possible) (8 days post initial transmission or 7 days post first day of first round of PRN). If the recovery criterion is met, subject is deemed as recovered and no further action is taken. If the recovery criterion is not met after second round of PRN, an Interim Report and Baseline Medication Report is sent by the ISCC nurse to the investigator for review and asked to re-evaluate the subject's chronic baseline medications (Right Arm of Figure 5)

In the event that it has been determined on initial subject contact, that the subject has been non-compliant with baseline medications for one or more days prior to contact, the subject will be instructed to take baseline medications for three days. Recovery criterion will be evaluated for effectiveness of reinstating baseline medications on day 4 and day 8 in the same fashion as described above. If recovery criterion is not met on either of these two evaluations, the first PRN will be initiated and the same schedule takes place and evaluation scheme thereafter is similar to as described above for a compliant subject except for a shift of at least 4 days.

If the subject has not been compliant with baseline medications but returning to baseline medications is not possible (e.g. unavailability of medications), subject will be instructed to contact their investigator immediately. An 'Interim Report' will be sent to the participating investigator (see Appendix B: ISCC Reports to Physician for an example of this report).

